Tools will be developed to facilitate SCC [session checklists, posters for the waiting and clinician rooms, pregnancy planning calendar, client SCM kits (needleless syringe, plastic cup, non-spermicidal condoms, lubricant), client pictorial instruction brochures (see appendix) and video demonstrations]. Guided by our consultant, [name], who has been using brief, simple SCM instructional videos created for use on Youtube by videotaping counseling role plays and testimonials of successful couples, we will create video clips for use in training FP nurses as well as to be used by the nurses to train clients, and for clients to refer to at home or where they can access the internet. These low cost videos can be made quickly and will be made using nurse role plays at first, but we will engage actual clients (with consent) who use the services over time. We will be particularly keen to engage male clients/partners in videos, as a way to foster male involvement.

(3) Routine screening of childbearing desires: To ensure clients receive either SCC or contraception as needed, a single question, “Are you thinking about trying to conceive a child within the next 12 months?” will be asked by expert clients at the triage station (which is where clients go after checking in for their visit) for all reproductive aged men (age 18-60) and women (age 18-45). The screening item is liberally worded so that it is inclusive of clients who are considering childbearing but may not be certain about their own desire or that of their partner, which will enable more clients to receive support from SCC to make an informed decision. Clients who report childbearing desires will be seen by a trained FP nurse for a SCC consult during the same clinic visit or scheduled for a future visit if the client is willing and able to bring their partner in for the consult. If the client is interested in participating in the study, the partner will need to come in for HIV testing prior to receiving the first SCC consult. Clients with no childbearing desires will be seen by the FP nurse for contraception.

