Routinely collected clinic data will be used to analyze FP services in the overall clinic population to examine clinic capacity and fidelity to the intervention. The triage book and childbearing screening item (in SCC1/SCC2 sites) will be used to determine: (a) # who do not want children and % receiving contraception services, and (b) # reporting childbearing desires. FP registries will indicate # new clients receiving FP services (not seen by FP in past year), and % of FP recipients using dual contraception. These will be tracked longitudinally to assess intervention effects on clinic level FP services. % of clients receiving FP referrals after triage will be compared across all 3 arms using research cohort data, since childbearing screening is not used at the usual care site.

Research Participants. The assigned FP programs at each study site will be implemented clinic-wide for all clinic clients, but the 66 study clients enrolled at each site will meet the following **eligibility criteria**:

1. Adults of reproductive age (men age 18-60; women age 18-45).
2. Considering childbearing with their spouse/partner. This will be determined via the triage screening item.
3. Reports having disclosed HIV status to partner. TASO counselors provide clients with assisted disclosure services to help them disclose to partners. Therefore, interested clients who have not yet disclosed their HIV status to their partner will be assisted to do so if they wish, after which they can be considered for enrollment.
4. Partner is HIV-negative. All couples can benefit from SCC and FP, but we focus on discordant couples due to the heightened value of SCC for reducing horizontal HIV transmission. We will use a rapid HIV test to confirm partner's status, and offer the option of a home-based test (a service offered by TASO) if necessary. Confirming the partner's status enables us to accurately assess intervention effects on seroconversion.

ART use is not an eligibility criterion, but SCC will be used to advise and support clients to start and adhere to ART before trying to conceive with SCM. TASO provides ART to all clients in serodiscordant relationships.

Note that only the HIV+ client will enroll in the study and participate in the survey research, not their partners.

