Recruitment. We will enroll 3-4 clients per month over 18 months at each site, which is feasible as >20 clients met this eligibility criteria in each recruitment month in our pilots. Recruitment will be stratified by sex to ensure a 50/50 gender balance, which will better enable us to examine intervention effects on partner seroconversion

and to gain the perspective of both male and female clients regarding fertility. We could enroll the sample more quickly, but the long enrollment period ensures we can recruit the target number of men, and enables us to have our 3 site coordinators manage three sites each (min. 1 day per week at each clinic) to limit personnel costs. Clients at the SCC1 and SCC2 sites who report at triage that they desire to have a child with a negative or unknown HIV status partner will be referred by triage to the site coordinator for screening. Screening (incl. partner HIV testing) and baseline survey will be completed prior to the initial SCC consultation. At the usual care site, the childbearing screening item will be included at triage only during the days of recruitment, which will be used to identify potential participants who will then be referred to the site coordinator for the same screening conducted at the intervention sites; the data from the screening item will not be placed in the client's chart or given to the FP nurse, as this screening is not part of usual care. Clients who decline to bring their partner in for HIV testing (but are otherwise eligible) and thus do not participate, will be asked to provide basic sociodemographic and partner characteristics in order to assess how they differ from the enrolled clients.

Data Collection

Assessment schedule: The baseline assessment will be done by the site coordinator once eligibility is confirmed, followed by assessments at months 6, 12, and post-pregnancy (if pregnancy occurs prior to month 12). To minimize attrition we will collect contact info (phone numbers and maps of homes), including contact information for family or friends who have frequent contact with the client. Clinic staff will also be able to help us track clients that we have difficulty reaching. In our current study we achieved 94% retention at Month 12.

Participant Compensation: Participants will receive 20,000 Ush (~\$6 USD) at each assessment.

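### The registry percentage of FP recipients on dual contraception has a case mix that the intervention itself changes, so it cannot be read as an intervention effect; cohort FP referral is a fidelity measure, not a clinic-level one

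*Combined protocol and SAP*

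**What the plan says.** In the combined protocol and SAP, under Process evaluation and clinic capacity/fidelity, the paragraph on routinely collected clinic data says these data serve "to examine clinic capacity and fidelity to the intervention". Two of its indicators matter here.

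- **Dual contraception.** The FP registries supply the percentage "of FP recipients using dual contraception. These will be tracked longitudinally to assess intervention effects on clinic level FP services". The denominator is not limited to clients who want to avoid pregnancy.
- **FP referral.** The percentage "of clients receiving FP referrals after triage will be compared across all 3 arms using research cohort data". The reason given is that the childbearing question is not part of routine triage at usual-care sites.

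Four other places determine who enters these denominators and numerators.

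- Arm 1, item (3), on routine screening: "Clients who report childbearing desires will be seen by a trained FP nurse for a SCC consult during the same clinic visit", or at a later visit if the partner can come. The same item adds: "Clients with no childbearing desires will be seen by the FP nurse for contraception".
- Arm 2: triage records the answer in the chart, and providers may then refer the client to the FP nurses.
- Arm 3: usual-care FP covers contraception and PMTCT, without SCC.
- Recruitment: at usual-care sites the question is asked on recruitment days only, and the answer is not charted "or given to the FP nurse, as this screening is not part of usual care".

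**The concern.** A percentage can be tracked as an intervention effect only if the intervention leaves its denominator alone, or if the denominator is restricted to people for whom the numerator is the goal. Neither holds for dual contraception. SCC adds clients to the FP nurses' caseload who, while they are trying to conceive, are not meant to be using dual contraception. An SCC site could therefore appear to provide worse contraceptive care than before, or than usual care, only because its FP caseload now includes people with a different goal.

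The plan conditions on intention elsewhere. The primary outcome depends on pregnancy intention (Measures), and the first triage indicator in the same paragraph concerns clients who do not want children. The dual-contraception indicator drops that condition.

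The referral indicator has a different problem, one of scope. It appears among analyses of the overall clinic population but is measured in a small group selected for considering childbearing, in which the arms are designed to differ. At stake is the process evaluation's account of capacity, fidelity and clinic-level effect.

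**Working it through.** The plan states no expected value or precision for either indicator, so there is no figure of its own to reproduce. The check is mixture arithmetic.

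**Inputs**

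- d = 11%: dual contraception among people living with HIV in Uganda who want to prevent pregnancy (Power analysis). Applying it to FP-registry contraception clients is an assumption.
- s: share of FP recipients who are SCC clients seeking conception. Not given; assumed 5% to 50%.
- n: share who are contraception clients newly brought in by screening. Not given; assumed 10% to 50%.
- d2: dual use among those newcomers. Not given; assumed 11% to 30%.
- Enrolled per site: 65 (Overview) or 66 (Research Participants). Clinic size: 6000 to 8000 (Study Setting).

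**Step 1: dilution with practice unchanged.** Observed percentage = d × (1 − s).

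| s | Observed |
|---|---|
| 5% | 0.11 × 0.95 = 10.5% |
| 10% | 0.11 × 0.90 = 9.9% |
| 20% | 0.11 × 0.80 = 8.8% |
| 30% | 0.11 × 0.70 = 7.7% |
| 50% | 0.11 × 0.50 = 5.5% |

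The relative fall equals s whatever d is: starting from 30%, the same 20% share gives 0.30 × 0.80 = 24%. Here s counts only clients still seeking conception. If 20% of recipients arrive through SCC, half of them choose contraception and their dual use is 11%, then s is 10% and the figure is 9.9%.

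**Step 2: adding the contraception clients found by the same screening.** Observed = d × (1 − s − n) + d2 × n. With s = 20% and n = 30%:

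- d2 = 11%: 0.11 × 0.50 + 0.11 × 0.30 = 8.8%
- d2 = 30%: 0.11 × 0.50 + 0.30 × 0.30 = 14.5%
- Break-even: d2 = d × (s + n) / n = 0.11 × 0.50 / 0.30 = 18.3%

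Over s and n each from 10% to 50%, the break-even runs from 0.11 × 0.60 / 0.50 = 13.2% to 0.11 × 0.60 / 0.10 = 66%. A fall is the likelier result, but a rise is possible.

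**Step 3: restricted denominator.** Among recipients not seeking conception, unchanged practice gives d × (1 − s) / (1 − s) = 11% at every s.

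**Step 4: the referral cohort.** It is 65/8000 = 0.8% to 66/6000 = 1.1% of a clinic's clients, all with a positive childbearing screen. The same entry condition applies in every arm, so with equal referral practice the difference between arms is zero. For illustration, assumed referral rates of 60% to 100% at SCC sites and 5% to 40% at usual care give a gap of 60 − 40 = 20 to 100 − 5 = 95 points. That gap comes from the numerator: the screen result is acted on in one setting and withheld in the other.

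**The case against.** Several arguments on the other side have force.

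- **Registry logging is not specified.** No section says that an SCC visit is entered in the FP registry, and separate SCC checklists and session logs exist. This stands as a condition on the point. Even so, the Overview places SCC within FP services, FP nurses deliver it, and the measures table groups FP and SCC consults under FP services used. Counting them as FP is the natural reading, and the silence is itself a reason to specify.
- **The direction is not fixed.** Screening also sends clients who want no child to the FP nurse. Contraception is advised until a couple agrees on childbearing, and some SCC clients then decide against a pregnancy. This stands: a reader might infer that the percentage must fall at SCC sites, and the documents do not support that. It does not rescue the indicator, because the second inflow is another way in which the intervention alters the denominator.
- **Companion indicators help.** Counts of clients wanting and not wanting children, and of new FP clients, would show some of the case mix. But the first two come from the screening item, which usual care does not routinely use.
- **Referral.** A reader might infer that enrolment biases the comparison in favour of SCC, or that referral looks better with no real change in service. Neither is supported. Usual care applies the same study screening, so the cohort is defined alike in every arm. Screening and referral are components of the intervention, so a higher rate is a real service difference, though a built-in one. A rate near 100% at SCC1 cannot be assumed either, since triage refers potential participants to the site coordinator and enrolment precedes the SCC consult. At SCC2, referral depends on providers acting on the chart, so the rate is informative about fidelity.
- **These are process measures**, with no hypothesis or decision rule attached. That limits the consequence, although the plan does say the registry indicators will be used to assess intervention effects.

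**Conclusion.** The point holds for dual contraception. As defined, the percentage mixes clients for whom dual contraception is the aim with clients for whom it is not, and the intervention changes that mix at SCC sites only. If SCC visits are counted as FP, unchanged practice at 11% would appear as 9.9%, 8.8% or 5.5% with conception-seekers at 10%, 20% or 50% of recipients. Those shares are assumptions, and newcomers with higher dual use could reverse the movement, so a change in either direction is uninterpretable as a service effect.

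For referral the point is one of labelling. The comparison describes about 1% of clinic clients, all considering childbearing, and its contrast with usual care is largely set by design. It is usable as fidelity in that group but does not measure clinic-wide referral.

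The consequence is confined to the process evaluation. The primary outcome is conditioned on pregnancy intention and is not touched.

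**What to change.** 1. Add a visit-type flag to the FP registry extract that separates SCC-only visits from contraception visits, and state how SCC visits are logged. The flag can follow the purpose of the visit, so usual-care sites need not introduce the screening question.
2. Report dual contraception among FP recipients not seeking conception, with the counts of SCC-only and contraception clients beside it at each time point. The restriction removes the dilution by conception-seekers. It does not remove the effect of newly screened-in contraception clients whose dual use differs, which is why the counts need to be shown.
3. Describe the cohort FP-referral comparison as a fidelity measure among clients with childbearing desires, and do not present it as a clinic-level effect. Referrals made at the enrolment visit should stay in: excluding them could discard the same-visit referral at SCC1 that the measure is meant to capture.

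The cost is one flag and slightly more tabulation from registries already in use. A rate per reproductive-age attendee would be a weaker alternative, because it still mixes in conception-seekers and SCC1's outreach might itself change attendance.

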able to successfully use SCM when the partner did not attend. The proposed study will provide data to answer this important question. In our pilot, most female partners attended SCC, but if not, she will be given a referral (via the male client) to come to TASO or the hospital FP clinic for contraception if they decide against childbearing; or if seeking childbearing the male will be asked to report on the timing of his partner's fertile period with information from his partner, or the nurse will phone the partner for this information with consent from the male. After conception, the FP nurse will provide PMTCT services; if clients have a miscarriage, the cause will be addressed if possible, than contraception or further SCC offered, as desired.

SCC Introductory Consultation (45-60 minutes):

- * Build rapport and supportive environment; encourage client/couple to express needs and expectations.
- * Discuss context related to readiness for childbearing (partner HIV status; HIV disclosure; partner's fertility desire; # of existing children; health of relationship; available resources/supports; work patterns separating the couple).
- * Review HIV and health risks of childbearing for mother, infant, & partner, & factors that contribute to or protect from risk (SCM; ART; CD4; PMTCT; STIs; alcohol use; nutrition). Encourage delaying pregnancy if medical condition not optimal (not on ART > 6 mos.; CD4<200; active STI) and provide treatment (for STIs, acute OIs, or ART) as needed.
- * Encourage client/couple to consider this information and take time to decide whether or not they want to have a child, and return the next week for either SCC or contraception counseling and services accordingly.

SCC Session 1 (20-30 minutes):

- * Review client/couple's decision: if no longer desire a child, provide contraception; otherwise continue with SCC.
- * Teach client to time the woman's ovulation period and fertile window using pregnancy calendar.
- * Client/couple receives instruction on selected SCM (TUI, or MSI if female HIV+ and male HIV-). Brochures and tool kit specific to the chosen method (e.g., condoms, lube, syringe, plastic cup) are given to client to take home; instructional video will be shown; SMS texts will be used to remind client of start of fertile period if they have a phone.

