Measures. Assessments will include measures of the primary and secondary outcomes and variables that map to our eIMB conceptual framework for understanding use of SCM and contraception, as listed below. Survey measures have been translated into Luganda in our prior research. The survey will be interviewer-administered using computer-assisted software, and administration time is 45-60 minutes.

Primary outcome: Correct use of contraception or SCM over the past 6 months, depending on pregnancy intentions; a single binary indicator will be created for use as the primary outcome, while continuous and categorical measures of frequency and duration of use will be used in secondary analyses. Correct use of contraception is defined as always using both condoms and another modern contraceptive (e.g., oral pills, DEPO injection, IUD implant) (i.e., dual contraception) over the past 6 months (since last survey), and will be ascertained via self-report and chart review (provision of non-condom contraceptive). Male participants will be asked to consent (it won't be required) to the coordinator calling their partner on the phone to assess use of non-condom contraceptives; these data will be kept confidential from the male. This definition is consistent with FP policy and practice in Uganda,⁶⁶ as condoms are important for HIV prevention, but used too inconsistently to prevent pregnancy, hence the need for an added contraceptive. If a participant becomes single or abstinent during the course of the study, avoiding pregnancy and use of contraception will be considered the desired behavior. The primary outcome will define whether SCM or contraception use was consistent (and changed to correspond with changes in pregnancy intentions) with pregnancy intentions over the entire study period.

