To assess correct SCM use, respondents will be asked if they used TUI, MSI, or sperm washing in the past 6 months and how often. Given the cost of sperm washing, TUI (applicable for all couples) and MSI (applicable for couples in which the male is HIV negative) are the two feasible methods for most clients. Clients will be asked in an open-ended format to describe exactly how they implemented the method. For each method, the interviewer will be looking for 3-5 pre-established pieces of information (e.g., identifying the timing of woman's fertile period; # of days in the fertile period; using condoms outside of the fertile period; collection of semen and insertion using syringe) from the participant's response, which will be used to rate the response as indicating "fully accurate" use of the method, "partially accurate" or no use. Only fully accurate use will be considered correct SCM use for the primary analysis, but the 3-level variable will be examined in secondary analysis. Social desirability may influence responses, but clients are not likely to be able to describe the method in such detail unless they are actually following the procedures. This assessment will occur prior to administering the SCM knowledge part of the survey (which uses a less detailed description of the method) to avoid biasing the measure of SCM use. We will ask about partner use of PrEP and male circumcision, but these methods will not be considered when rating proper SCM use since they are not specific to the context of conception.

Secondary outcomes: (1) achievement of desired pregnancy status and pregnancy outcome [live birth or miscarriage (we will not be able to adequately assess induced abortions due to strong stigma and illegality of such abortions, making it very difficult to get accurate data)] assessed via self-report and chart abstraction; (2) partner seroconversion, with HIV testing at month 12 in addition to testing as part of SCC); (3) PMTCT adherence (enrollment by 14 weeks gestation, ART use during pregnancy and post-delivery, infant ART

prophylaxis, and early infant diagnosis of HIV) for those who become pregnant, assessed via chart abstraction; (4) self-reported consistent condom use in past 6 months (generally for those not seeking childbearing, and all times outside of 3-day fertile period of each month for those seeking childbearing and using TUI/MSI).

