Power analysis: 11% of PLHA in Uganda who want to prevent pregnancy use dual contraception³⁰ and our research shows 15% of PLHA trying to conceive use TUI or MSI.³⁷ Therefore, we expect the usual care arm will have a 15% rate of correct use of contraception/SCM (depending on pregnancy intentions), which is the primary outcome. Using an intra-class correlation (ICC) of 0.01 to control for clustering, based on other studies of reproductive health outcomes,⁷⁴ and 10% attrition at Month 12 (given the 6% in our current study), we will have > 80% power (2-tailed test) to detect a 4.5 percentage point difference (small effect size; $d=.15$) for our comparison of the usual care arm to the combined SCC1 & SCC2 arms on the use of contraception or SCM at month 12, and a 7-8 percentage point difference between the SCC1 and SCC2 intervention arms. In analysis of effects on contraception and SCM use separately, and with half the sample expected to decide to pursue pregnancy and half contraception based on our pilot data, our sample size will provide > 80% power to detect a 6.5 percentage point difference with regards to each of the outcomes when comparing usual care to SCC1 and SCC2 combined, and 8-9 percentage point difference between the SCC1 and SCC2 interventions.

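### The primary outcome's time windows are not reconciled into one scoring rule, and time spent pregnant is not scored at all

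*Combined protocol and SAP*

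**What the plan says.** The combined protocol and SAP speaks to this in five places.

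- **Measures, Primary outcome.** The outcome is "Correct use of contraception or SCM over the past 6 months, depending on pregnancy intentions; a single binary indicator will be created". Correct contraception means dual use, without lapse, "over the past 6 months (since last survey"). The paragraph closes by saying that the outcome captures whether use was consistent "with pregnancy intentions over the entire study period", allowing for intentions that change. Special scoring is given only for clients who become single or abstinent.
- **Measures, correct SCM use.** The client describes how the method was carried out and the interviewer rates the description. "Only fully accurate use will be considered correct SCM use for the primary analysis".
- **Data Collection, Assessment schedule.** Baseline is "followed by assessments at months 6, 12, and post-pregnancy (if pregnancy occurs prior to month 12").
- **Data Analysis Plan.** The Power analysis sets the comparison "on the use of contraception or SCM at month 12", with a 15% usual-care rate. The Data analysis section refers back to the Measures definition. It leaves outcomes based on frequency of correct use through the study to exploratory work.
- **Arm 1, structured sessions.** "After conception, the FP nurse will provide PMTCT services". If there is a miscarriage the cause is addressed where possible, "than contraception or further SCC offered, as desired".

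**The concern.** A binary primary endpoint should follow from the plan without the analyst having to choose. Here two choices are open: which survey or surveys decide success, and what to do with months in which the client, or a male client's partner, is pregnant.

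The second gap matters because pregnancy is an intended result for many participants. All enter considering childbearing, and the Power analysis expects about half to pursue it. During pregnancy a couple is no longer trying to conceive with SCM and has no reason to use dual contraception, so neither component of the outcome applies as defined. A client who did what the intervention teaches could be coded as not having done it. If the rule were settled after data are seen, the choice could move the result. Dropping conceivers instead would condition the analysis on an event after randomisation.

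**Working it through.** **1. The plan's own figure.** The Overview gives 2 sites per arm and 65 clients per site. The Power analysis gives 10% attrition, an ICC of 0.01, a 15% control rate and a 4.5-point difference. Alpha is not stated; I assume 0.05 two-sided.

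- Retained per site: 65 × 0.9 = 58.5.
- Design effect: 1 + (58.5 − 1) × 0.01 = 1.575.
- Effective sample: 117/1.575 = 74.3 usual care against 234/1.575 = 148.6 combined.
- Power for 15% against 19.5% (pooled normal approximation): about 12%, not above 80%.

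That is a separate matter. Below, 4.5 points is only the plan's stated target, not a difference the trial is shown to detect.

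**2. One client under three readings.** Assume a 9-month pregnancy. The client uses SCM with full accuracy and conceives at month 3; the pregnancy ends at month 3 + 9 = 12. There are 3 months of SCM use in months 0–6 and none in months 6–12.

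| Rule | Months 0–6 | Months 6–12 | Score |
|---|---|---|---|
| Correct at month 12 | not used | neither method | failure |
| Correct at both surveys | correct | neither method | failure |
| Correct at either survey | correct | neither method | success |

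This needs no assumed rate. By contrast, conception at month 8 leaves 8 − 6 = 2 months of SCM use in the second window. That could count as correct, because the SCM rating rests on how the method was carried out and not on use throughout the window.

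**3. Effect of the combining rule on the control rate.** Let p = 15% be correct in each window and ρ the within-client correlation, which the documents do not give. Then P(both) = p² + ρp(1 − p) and P(either) = 2p − P(both).

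| ρ (assumed) | Month 12 only | Both | Either |
|---|---|---|---|
| 0 | 15% | 2.25% | 27.75% |
| 0.5 | 15% | 8.6% | 21.4% |
| 1 | 15% | 15% | 15% |

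So the 15% planning rate has no fixed meaning until the rule is named.

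**4. Illustrative attenuation under the month-12 reading.** Let c be the share of correct SCM users who conceive too early to have scorable use in months 6–12. It is assumed equal in all arms. Half of each arm seeks pregnancy, and without early conception the rates in both halves are 15% and 19.5%. If early conceivers are coded as failures, the observed difference is 0.5 × 4.5 × (1 − c) + 0.5 × 4.5 = 4.5 × (1 − c/2).

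- c = 10%: 4.275 points, a loss of 0.225 (5%).
- c = 30%: 3.825 points, a loss of 0.675 (15%).
- c = 50%: 3.375 points, a loss of 1.125 (25%).

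**5. Illustrative effect of the pregnancy coding.** Suppose no behavioural effect (15% correct among the non-pregnant in every arm) and, purely as an assumption, 20% pregnant in usual care against 30% in the intervention arms.

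- Pregnant coded as failure: 0.15 × 0.70 − 0.15 × 0.80 = 10.5% − 12.0% = −1.5 points.
- Pregnant excluded: 15% − 15% = 0.
- Pregnant coded as success: (10.5% + 30%) − (12.0% + 20%) = +8.5 points.

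**The case against.** The best defence is that the definition is looser than it is incomplete. The six-month phrase can be read as each survey's recall period, the whole-study phrase as the way surveys are put together, and month 12 as the time when that is complete. This has force. A reader might infer that the plan has no combining rule of any kind; the documents do not support that, because the closing sentence of the primary outcome paragraph states a principle and, taken literally, points towards consistency in every window. What remains is that this is not an algorithm, and that it sits beside two other windows without being reconciled to them.

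A reader might also infer that the plan requires conceivers to be scored as failures. It does not. Someone who wanted a pregnancy, used SCM correctly and conceived has acted in line with intention, and the text can be read that way. Failure is one literal reading; the accurate description is that the score is unspecified.

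Nor do the documents show that conception will mostly come early. The six-month limit in the Arm 1 follow-up sessions counts months of correct SCM use, not months since enrolment, and it describes SCC1 only. Other parts of Arm 1 push conception later: contraception is recommended until the couple agree, and delay is encouraged when health is not optimal. The affected share could be small.

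Finally, the post-pregnancy survey has a natural use for the PMTCT secondary outcome. A conception at month 11 would end at about month 20 (11 + 9), which shows that the survey's role needs stating. It does not show that the survey damages the primary outcome.

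**Conclusion.** The point stands in this form: the windows are not reconciled, a principle is given without an algorithm for combining the month-6 and month-12 surveys, and no section scores pregnant time. Under two of the three natural readings, a client who used SCM correctly, conceived before month 6 and stayed pregnant is coded as a failure. The need for a change rests on the indicator not being uniquely derivable, which requires no assumed rate.

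The size of any bias is unknown. The range of 4.3 to 3.4 points for a 4.5-point difference depends on an assumed early-conception share of 10% to 50%, equal across arms, an equal split of intentions in each arm, and the failure coding. The change of sign in step 5 depends on assumed pregnancy rates that differ by arm. Neither is a prediction for this trial.

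**What to change.** - Name one primary window, state the rule that combines the month-6 and month-12 surveys, and make the other window secondary.
- Say which window the 15% control rate refers to, and restate it if it does not match the one chosen.
- Exclude pregnant person-time from scoring. Score conceivers on SCM or contraception use against stated intention up to conception, and again after the pregnancy ends if that falls in the window, for example after a miscarriage. Do not code them as non-users and do not drop them.
- If months 6–12 is the chosen window, say that a client with no scorable time in it is scored on the pre-conception period; otherwise the exclusion would simply turn failures into missing values.
- State whether a post-pregnancy survey held after month 12 enters the primary outcome.
- Add a sensitivity analysis with the alternative codings of conceivers.

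The cost is wording and derivation code, with no new visits. There are real downsides. Conceivers are scored over a shorter and earlier period, which may differ by arm; the sensitivity analysis is there for that reason. Conception dates must come from the self-report and chart data already planned for pregnancy status. Because partners are not enrolled, dates for male clients lean more on self-report. An early conceiver who misses the month-6 survey may have no pre-conception data.

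Whether single or abstinent clients must also use contraception to count as successes is a separate clarification.
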